7.4.3 Independent Monitoring Committee (IMC)

The protocol will also have an Independent Monitoring Committee (IMC), consisting of the Principal Investigator and two independent, qualified investigators who are outside of the Laboratory of Molecular Biology (LMB) branch and are not involved in the study. The committee will meet after the first 5 subjects have been treated and completed the DLT evaluation window. The IMC will review adverse events and other associated safety data (this review may occur prior to the first annual continuing review date). The committee will be responsible for deciding whether treatment can proceed under the current protocol, whether protocol modifications are required for study continuation, or whether the protocol should be closed to further accrual due to toxicity of the study agents. The IMC may be convened for an ad hoc evaluation of protocol safety by the Principal Investigator or at the request of the IRB or SMC at other occasions during the study if concerns about study drug or research protocol safety or toxicity arise.

The minutes of the IMC meetings will be submitted to the IRB at the time of continuing review, unless an issue arises that requires prompt reporting to the IRB and then results will be submitted more expeditiously.

8 SPONSOR SAFETY REPORTING

8.1 **DEFINITIONS**

8.1.1 Adverse Event

Any untoward medical occurrence in a patient or clinical investigation subject administered a pharmaceutical product and which does not necessarily have a causal relationship with this treatment. An adverse event (AE) can therefore be any unfavorable and unintended sign (including an abnormal laboratory finding), symptom, or disease temporally associated with the use of a medicinal (investigational) product, whether or not related to the medicinal (investigational) product (ICH E6 (R2).

8.1.2 Serious Adverse Event (SAE)

An adverse event or suspected adverse reaction is considered serious if in the view of the investigator or the sponsor, it results in any of the following:

- Death,
- A life-threatening adverse event (see Section **8.1.3**)
- Inpatient hospitalization or prolongation of existing hospitalization

- A hospitalization/admission that is pre-planned (i.e., elective or scheduled surgery arranged prior to the start of the study), a planned hospitalization for pre-existing condition, or a procedure required by the protocol, without a serious deterioration in health, is not considered a serious adverse event.
- A hospitalization/admission that is solely driven by non-medical reasons (e.g., hospitalization for patient convenience) is not considered a serious adverse event.
- Emergency room visits or stays in observation units that do not result in admission to the hospital would not be considered a serious adverse event. The reason for seeking medical care should be evaluated for meeting one of the other serious criteria.
- Persistent or significant incapacity or substantial disruption of the ability to conduct normal life functions
- A congenital anomaly/birth defect.
- Important medical events that may not result in death, be life-threatening, or require hospitalization may be considered a serious adverse drug experience when, based upon appropriate medical judgment, they may jeopardize the patient or subject and may require medical or surgical intervention to prevent one of the outcomes listed in this definition.

8.1.3 Life-threatening

An adverse event or suspected adverse reaction is considered "life-threatening" if, in the view of either the investigator or sponsor, its occurrence places the patient or subject at immediate risk of death. It does not include an adverse event or suspected adverse reaction that, had it occurred in a more severe form, might have caused death. (21CFR312.32).

8.1.4 Severity

The severity of each Adverse Event will be assessed utilizing the CTCAE version 5.

8.1.5 Relationship to Study Product

All AEs will have their relationship to study product assessed using the terms: related or not related.

- Related There is a reasonable possibility that the study product caused the adverse event. Reasonable possibility means that there is evidence to suggest a causal relationship between the study product and the adverse event.
- Not Related There is not a reasonable possibility that the administration of the study product caused the event.

8.2 Assessment of Safety Events

AE information collected will include event description, date of onset, assessment of severity and relationship to study product and alternate etiology (if not related to study product), date of resolution of the event, seriousness and outcome. The assessment of severity and relationship to the study product will be done only by those with the training and authority to make a diagnosis and listed on the Form FDA 1572 as the site principal investigator or sub-investigator. AEs

occurring during the collection and reporting period will be documented appropriately regardless of relationship. AEs will be followed through resolution.

SAEs will be:

- Assessed for severity and relationship to study product and alternate etiology (if not related to study product) by a licensed study physician listed on the Form FDA 1572 as the site principal investigator or sub-investigator.
- Recorded on the appropriate SAE report form, the medical record and captured in the clinical database.
- Followed through resolution by a licensed study physician listed on the Form FDA 1572 as the site principal investigator or sub-investigator.

For timeframe of recording adverse events, please refer to Section 6.1. All serious adverse events recorded from the time of first investigational product administration must be reported to the sponsor.

8.3 **Reporting of Serious Adverse Events**

Any AE that meets a protocol-defined serious criteria or meets the definition of Adverse Event of Special Interest that require expedited reporting must be submitted immediately (within 24 hours of awareness) to OSRO Safety using the CCR SAE report form.

All SAE reporting must include the elements described in Section 8.2.

SAE reports will be submitted to the Center for Cancer Research (CCR) at: [contact] and to the CCR PI and study coordinator. CCR SAE report form and instructions can be found at:

https://ccrod.cancer.gov/confluence/pages/viewpage.action?pageId=157942842

Following the assessment of the SAE by OSRO, other supporting documentation of the event may be requested by the OSRO Safety and should be provided as soon as possible.

8.4 **Reporting Pregnancy**

8.4.1 Maternal exposure

If a patient becomes pregnant during the course of the study, the study treatment should be discontinued immediately, and the pregnancy reported to the Sponsor no later than 24 hours of when the Investigator becomes aware of it. The Investigator should notify the Sponsor no later than 24 hours of when the outcome of the Pregnancy become known,

Pregnancy itself is not regarded as an SAE. However, congenital abnormalities or birth defects and spontaneous miscarriages that meet serious criteria (see Section 8.1.2) should be reported as SAEs.

The outcome of all pregnancies (spontaneous miscarriage, elective termination, ectopic pregnancy, normal birth, or congenital abnormality) should be followed up and documented.

8.4.2 Paternal exposure

Male patients should refrain from fathering a child or donating sperm during the study and for 3 months after the last dose of study drugs.

Pregnancy of the patient's partner is not considered to be an AE. However, the outcome of all pregnancies (spontaneous miscarriage, elective termination, ectopic pregnancy, normal birth, or congenital abnormality) occurring from the date of the first dose until 3 months after the last dose should, if possible, be followed up and documented.

8.5 REGULATORY REPORTING FOR STUDIES CONDUCTED UNDER CCR-SPONSORED IND

Following notification from the investigator, CCR, the IND sponsor, will report any suspected adverse reaction that is both serious and unexpected in expedited manner to the FDA in accordance to 21 CFR 31.2.32. CCR will report an AE as a suspected adverse reaction only if there is evidence to suggest a causal relationship between the study product and the adverse event. CCR will notify FDA and all participating investigators (i.e., all investigators to whom the sponsor is providing drug under its INDs or under any investigator's IND) in an IND safety report of potential serious risks from clinical trials or any other source, as soon as possible, in accordance to 21 CFR Part 312.32.

All serious events will be reported to the FDA at least annually in a summary format.

9 CLINICAL MONITORING

As a sponsor for clinical trials, FDA regulations require the CCR to maintain a monitoring program. The CCR's program allows for confirmation of study data, specifically data that could affect the interpretation of primary and secondary study endpoints; adherence to the protocol, regulations, ICH E6, and SOPs; and human subjects protection. This is done through independent verification of study data with source documentation focusing on:

- Informed consent process
- Eligibility confirmation
- Drug administration and accountability
- Adverse events monitoring
- Response assessment.

The monitoring program also extends to multi-site research when the CCR is the coordinating center.

This trial will be monitored by personnel employed by a CCR contractor. Monitors are qualified by training and experience to monitor the progress of clinical trials. Personnel monitoring this study will not be affiliated in any way with the trial conduct.

10 STATISTICAL CONSIDERATIONS

10.1 STATISTICAL HYPOTHESIS

10.1.1 Primary Endpoints

The primary endpoint of the dose escalation phase is to identify the MTD and the desirable dose of LMB-100 with tofacitinib.

The primary endpoint of the expansion phase is to determine the number of participants that meet a threshold serum drug concentration during cycle 2 of treatment. The threshold drug level has been set at >600 ng/mL as measured at EOI for any LMB-100 administration during the cycle of interest.

10.1.2 Secondary Endpoints

The secondary endpoints for both the dose expansion and dose escalation cohorts are the LMB-100 peak serum level, half-life and AUC during cycle 1, and the percentage of participants with EOI LMB-100 serum drug concentration that meets threshold during cycle 3. For the dose escalation cohort, the percentage of participants with EOI LMB-100 serum drug concentration that meets threshold during cycle 2 of treatment will also be measured. For the dose expansion cohort, the number and description of adverse events by grade will also be reported.

10.2 SAMPLE SIZE DETERMINATION

The primary endpoints of this trial are to 1) identify the MTD and the desirable dose of the tofacitinib + LMB-100 combination format and 2) to determine whether the combination results in 80% of patients achieving threshold drug levels during cycle 2 of LMB-100. The MTD is defined as the maximum dose at which less than 33% of patients experience a DLT. The desirable dose will be selected from among the dose levels at or below the MTD. A lower dose than the MTD might be assessed in the expansion phase if chronic toxicity of LMB-100 is judged to be intolerable by the investigator at the MTD.

As per standard 3+3 design, if 0 of 3 or <2 of 6 patients experience DLT then dose escalation may proceed. If 2 or more patients experience DLT at any dose level, then dose de-escalation is required.

Dose escalation will proceed from dose level 1 to 2. If 0 of 3 or 0-1 of the first 6 patients in dose level 1 have a DLT, then dose escalation will proceed to dose level 2. Alternatively, if 2 or more patients in level 1 experience DLT, then dose will be de-escalated to dose level -1.

Based on two dose levels, the theoretical maximum number of subjects that can enroll on the dose escalation would be 12 (6 patients per level x2 dose levels).

Following completion of the dose escalation, enrollment of an additional 15 patients with pancreatic cancer or extrahepatic cholangiocarcinoma will be undertaken to better assess the a) safety of the optimal dose in the target population, and b) ability of tofacitinib to delay development of ADAs against LMB-100 and result in serum LMB-100 drug levels reaching threshold in cycle 2 and beyond. Participants on the dose escalation arm who are treated at MTD and meet eligibility requirements for the dose expansion phase can be counted towards the 15 patients needed to accrue to the expansion phase. We estimate that as many as 50% of patients

who start treatment will develop progressive disease by restaging after 2 cycles and would therefore be uninformative for assessing the longer-term immunogenicity endpoint. Thus, additional patients may be needed to complete the evaluation of toxicity and possible efficacy at the escalating dose levels.

This evaluation in 15 patients of either histology (but at least 8 patients in this expansion phase must have pancreatic adenocarcinoma) will be undertaken using the following guidelines: The objective will be to determine if the fraction of patients who are able to achieve threshold levels of LMB-100 in cycle 2 is consistent with 80% and greater than 50%. If 15 evaluable patients are enrolled, and if 11 or more patients meet threshold drug levels in cycle 2, then the probability of this occurring is 5.9% if the true probability of achieving threshold drug levels in cycle 2 were 50% and the probability of this occurring is 83.6% if the true probability of achieving threshold drug levels in cycle 2 were 80%. Thus, the expansion phase would be considered to have a positive outcome if 11 or more of 15 patients in the expansion phase achieve threshold drug levels. In practice, after the trial has ended accrual, the fraction of evaluable patients assessed during the expansion phase that achieve threshold drug levels in cycle 2 will be determined and reported along with two-sided 80% and 95% confidence intervals to aid in interpretation of the results. The fraction of patients who achieve threshold drug levels in cycle 3 will also be reported along with a 95% confidence interval, but this may be a small fraction and will be interpreted as being an exploratory evaluation.

As an early stopping rule, if after the first 5 evaluable patients in the expansion cohort have been treated, 0 of the 5 achieve threshold drug levels in cycle 2, then no further patients will be accrued as soon as that can be determined, with no pause in accrual, since this would be inconsistent with the goal of having 11 or more of 15 patients achieving threshold drug levels in cycle 2.

With up to 12 patients in the dose escalation phase and 15 in the expansion cohort, a maximum of 27 evaluable patients are required to complete accrual to this study. The accrual ceiling will be set at 45 patients to account for screen failures or patients who are treated but unable to complete the DLT period. It is anticipated that up to two patients per month may enroll onto this trial. Thus, accrual is expected be completed in approximately 2 years.

10.3 POPULATIONS FOR ANALYSES

10.3.1 Evaluable for toxicity

All patients who receive treatment during dose escalation will be reported. Any patient who receives any study drug treatment and experiences a DLT related to study drug within 21 days of initial treatment is evaluable. Otherwise, patients evaluable for DLT must: 1) receive all doses of study drugs, 2) be followed for study drug toxicity for at least 21 days after the administration of the first dose of LMB-100.

In the expansion phase, up to 15 evaluable patients who can have their drug levels assessed in cycle 2 will be included in analyses. Up to 5 patients will be replaced if they have PD before C2, but if more than 5 patients progress before C2, then no further patients will be accrued as soon as this can be determined.

10.3.2 Evaluable for objective response:

Only those patients who have measurable disease present at baseline, have received at least one cycle of therapy, and have had their disease re-evaluated will be considered evaluable for response. These patients will have their response classified according to the definitions stated below. (Note: Patients who exhibit objective disease progression prior to the end of cycle 1 will also be considered evaluable.) Responses or progressions noted in patients receiving treatment extension will be recorded in the study database but will not be reported in the aggregate objective response rate, which only corresponds to assessments taken prior to the start of a 4th cycle.

10.3.3 Evaluable Non-Target Disease Response:

Patients who have lesions or tumor marker present at baseline that are evaluable but do not meet the definitions of measurable disease, have received at least one cycle of therapy, and have had their disease re-evaluated will be considered evaluable for non-target disease. The response assessment is based on the presence, absence, or unequivocal progression of the lesions or increase in tumor marker.

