3.1.1 Dose Limiting Toxicity

For the study, a DLT will be defined as any of the following events occurring during the first cycle of treatment (21 days), the DLT evaluation period. Toxicities determined to be unequivocally related to disease progression or intercurrent illness will not be regarded as DLTs. The following will be considered DLTs:

- Any death not clearly due to the underlying disease or extraneous causes
- Transaminitis that meets criteria for Hy's Law: grade ≥2 elevation of AST or ALT with simultaneous elevation of total bilirubin to ≥ 2x ULN while alkaline phosphatase remains < 2x ULN.

Hematological toxicities:

- Grade 4 neutropenia (i.e. absolute neutrophil count (ANC) <0.5 x 10^3 cells/µL for a minimum duration of 7 days)
- Grade 3 and 4 febrile neutropenia (i.e. ANC < 1.0×10^3 cells/µL with a single temperature of >38.3°C or a sustained temperature of ≥38°C for more than one hour; or life-threatening consequences with urgent intervention indicated)
- Grade 4 thrombocytopenia ($\leq 25.0 \times 10^3 \text{ cells/}\mu\text{L}$)
- Grade 3 thrombocytopenia associated with bleeding episodes
- Grade 4 anemia

$\underline{\text{Grade} \geq 3 \text{ non-hematological toxicity with the exception of:}}$

- Grade 3 nausea and vomiting lasting <48 hours occurring in the absence of appropriate anti-emetic treatment
- Grade 3 diarrhea lasting for ≤ 2 days with no fever or dehydration
- Infusion-related reactions up to and including Grade 3. IRRs are not considered to be DLTs since, based on experience with monoclonal antibodies, they are idiosyncratic and not dose-related events. Precautions will be taken if IRRs Grade ≥2 occur (see Section 3.3).
- Asymptomatic grade 3 elevation of ALT, AST, GGT, bilirubin or alkaline phosphatase attributable to study drug that persists for less than 7 days if not violating Hy's Law. (Please note that all grade 4 elevations in these parameters should be considered a DLT)
- Asymptomatic laboratory values (other than ALT, AST, GGT, bilirubin, alkaline phosphatase or creatinine) of Grade 3 that are judged not clinically significant by the investigator.
- Isolated Grade 3 fever (without signs and/or symptoms of an infection) occurring within 48 hours after LMB-100 infusion and resolving within 48 hours to \leq Grade 2 and fully resolved within 1 week.

Other toxicities:

- Any other drug related toxicity considered significant enough to be qualified as a DLT in the opinion of the principal investigator.

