- Inability to start cycle 2 within 2 weeks after completing cycle 1 due to drug-related adverse events.

If a participant experiences a DLT of any grade, the investigator will have the option to either stop treatment or to resume the treatment at the next lowest dose level based on best clinical judgment. Patients will be assessed based on the original cohort. This can be done to allow participants who could potentially benefit from LMB-100 to remain on the study drug treatment, if considered the most beneficial therapeutic option for the participant while managing and monitoring the participant's safety risks.

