10.4.4 Safety Analyses

Safety will be evaluated during the dose escalation phase and will include reporting toxicities by grade and type at each dose level in addition to DLTs.

During the 15-patient expansion cohort, the following rule will be used: Within the initial 6 patients, no more than 1 patient in 6 is permitted to experience a DLT attributable to study agents. After the initial 6 patients, safety will be monitored continuously per the following rule: if the cumulative fraction of patients enrolled who experience a DLT attributable to study agents is 1/6 or less, patients will be allowed to continue to enroll onto this protocol.

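### Section 10.3.1 can make a patient with a doubtful-cause DLT under 3.1.1 non-evaluable, which can tilt the 3+3 toward clearing a dose; separately, 10.4.4 sets a more lenient DLT test in the expansion

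*Combined protocol and SAP*

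**What the plan says.** **Section 3.1.1 (definition).** A DLT is any listed event "occurring during the first cycle of treatment (21 days), the DLT evaluation period". The general exclusion is narrow: "Toxicities determined to be unequivocally related to disease progression or intercurrent illness will not be regarded as DLTs". For deaths the listed item is "Any death not clearly due to the underlying disease or extraneous causes". Only two items require a link to drug: "Any other drug related toxicity considered significant enough to be qualified as a DLT in the opinion of the principal investigator" and "Inability to start cycle 2 within 2 weeks after completing cycle 1 due to drug-related adverse events".

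**Section 10.3.1 (evaluability).** Any patient who has received some study drug and "experiences a DLT related to study drug within 21 days of initial treatment is evaluable". All others must have received every dose of both drugs and been followed for toxicity for at least 21 days after the first LMB-100 dose.

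**Section 10.4.4 (expansion monitoring).** Among the first six patients, "no more than 1 patient in 6 is permitted to experience a DLT attributable to study agents". After that, enrolment continues while the cumulative fraction with such a DLT is 1/6 or less.

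**Section 8.1.5 (causality).** An event is related if there is a reasonable possibility, meaning some evidence, of a causal link. It is not related when "There is not a reasonable possibility that the administration of the study product caused the event".

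**Rules that set the MTD.** Section 3.1.2 with Table 9, Section 10.2 and Section 10.4.2 refer to DLTs without any attribution qualifier.

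**The concern.** Section 3.1.1 presumes that a listed event is a DLT and asks for proof of another cause before removing it. Sections 10.3.1 and 10.4.4 ask for a positive attribution to drug. An event of uncertain cause can meet the first test and fail the second.

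Such events are foreseeable here. Section 1.2.12 says that tofacitinib may raise the risk of venous thromboembolism and that pancreatic cancer is itself highly pro-thrombotic. The exclusion criteria name cholangitis as an infection of concern because tofacitinib impairs the host response.

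Identifying the MTD is a primary endpoint, and cohorts are of three to six patients. If the patient with the only DLT among three becomes non-evaluable and is replaced by a patient without one, 1/3 becomes 0/3. The level is then cleared without the extra patients, or the stop at the investigator's discretion, that Table 9 provides for 1/3.

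**Working it through.** **1. The plan's own figures.** The only operating characteristics stated are for the expansion efficacy rule (11 or more of 15). The exact binomial gives 0.0592 at a 50% rate and 0.8358 at 80%, matching the stated 5.9% and 83.6%. This point does not affect them. The plan states none for the 3+3.

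**2. Which doubtful DLTs are lost.** Take an event that meets 3.1.1 but is coded not related.

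- *Death in the 21-day window.* The first LMB-100 dose is on Day 4, so 21 days of follow-up runs to about Day 25 (4 + 21). The condition cannot be met and the patient is non-evaluable.
- *Non-fatal event that prevents any dose of LMB-100 (to Day 8) or tofacitinib (to Day 10).* The all-doses condition fails and the patient is non-evaluable.
- *Non-fatal event in a patient who receives all doses and completes follow-up.* The patient is evaluable and the DLT counts.

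Section 10.2 sets the accrual ceiling at 45, against 27 evaluable patients, partly to allow for treated patients who do not complete the DLT period. Replacement is therefore foreseen.

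**3. Effect on the 3+3.** Let p be the rate of 3.1.1 DLTs and f the fraction of them that is lost and replaced. Neither is in the documents, so both are assumed. Among evaluable patients the rate becomes

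p* = p(1 − f) / (1 − pf).

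Taking a 1/3 result as always expanded to six, the chance of clearing a level is

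P = (1 − p*)³ + 3p*(1 − p*)² × (1 − p*)³.

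At p = 0.30:

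- f = 0: 0.343 + 0.151 = 0.494.
- f = 1/3: p* = 0.20/0.90 = 0.222, P = 0.660.
- f = 1/2: p* = 0.15/0.85 = 0.176, P = 0.759.

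Other values of P:

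| True rate p | f = 0 | f = 10% | f = 25% | f = 50% |
|---|---|---|---|---|
| 20% | 70.9% | 74.4% | 79.8% | 88.7% |
| 33% | 43.4% | 48.0% | 55.7% | 71.4% |
| 40% | 30.9% | 35.1% | 42.8% | 60.0% |
| 50% | 17.2% | 20.3% | 26.5% | 42.8% |

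If f is read as the share of DLTs that are doubtful and coded not related, these are upper values, because every such event is taken to cost evaluability. At p = 33% with 25% of DLTs doubtful, P is 43.4% if none of those patients becomes non-evaluable, 49.2% if half do and 55.7% if all do.

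**4. Effect on the expansion limit.** Section 10.4.4 uses patients enrolled, so a patient whose DLT is not attributed stays in the denominator and the rate is p(1 − f). With r for that rate, the chance of at most 1 DLT in 6 is (1 − r)⁶ + 6r(1 − r)⁵. At p = 33%:

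- f = 0: r = 0.33, 35.8%.
- f = 10%: r = 0.297, 42.7%.
- f = 25%: r = 0.2475, 54.0%.
- f = 50%: r = 0.165, 74.1%.

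**The case against.** The strongest reply is that 10.3.1 decides who is evaluable and does not redefine a DLT. This stands, and it limits the point. A reader might infer that every event of doubtful cause drops out and that the MTD is therefore biased upward. The documents do not support that: Table 9, 10.2 and 10.4.2 count DLTs without qualification, and a patient who completes dosing and follow-up keeps the DLT. Only events that cut short dosing or follow-up are exposed.

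A reader might also infer that 10.4.4 distorts the MTD. It governs only the expansion cohort, which opens after escalation is complete. Section 10.2 does let eligible patients treated at the MTD count toward the 15, so one event could be judged under both standards, but the MTD is already set by then.

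A larger effect is also tempting. Using p(1 − f) for escalation at p = 0.30 gives 71% (f = 1/3) and 81% (f = 1/2). That keeps the patient in the cohort as a non-DLT. Under 10.3.1 the patient is non-evaluable and is replaced, which gives 66% and 76%. If only half of the doubtful events cost evaluability (f = 1/6 and 1/4), the figures are about 57% and 61%.

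The gap may be small in practice. The threshold for related in 8.1.5 is low, and the protocol itself links tofacitinib to thrombosis and impaired response to infection, so an investigator may well code such events as related. Weekly team review (7.4.1) and the Independent Monitoring Committee's review after the first five subjects (7.4.3) would probably examine a doubtful death. These are real safeguards, but they do not say which wording governs the count.

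**Conclusion.** The point holds in limited form. Applied literally, 10.3.1 can remove a DLT that 3.1.1 counts from a cohort of three to six patients. It does so when the cause is doubtful, the event is coded not related, and dosing or follow-up is cut short, as always happens with a death in the DLT window. In escalation the direction is always toward clearing the dose.

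The size rests on assumed rates: from 49% to at most 66% or 76% at a 30% DLT rate with one third or one half lost, and from 43% to between 48% and 71% at 33% with 10% to 50% lost. It is zero if no doubtful event makes a patient non-evaluable. The calculation also assumes that related in 10.3.1 carries its 8.1.5 meaning and that non-evaluable patients are replaced.

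Separately, the expansion limit is more lenient than the escalation standard. At a 33% rate, the chance of passing the first six patients rises from 36% to between 43% and 74% if 10% to 50% of DLTs are judged not attributable. The MTD is unaffected by this.

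**What to change.** Reconcile the sections so that one DLT definition applies throughout. In 10.3.1, drop the drug-relation qualifier and refer to a DLT as defined in Section 3.1.1. In 10.4.4, make both mentions of a DLT refer to the same definition. Keep all of 3.1.1's exclusions, including the one for intercurrent illness, and its two drug-related items.

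The cost is three phrases in the protocol. The downside is small: a few events of doubtful cause will count against a dose level or the expansion limit.
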